6.3. Lifestyle Restrictions

Study patients must be instructed not to donate blood or blood products during the study and for 8 weeks following the last dose of study drug.

The following patients must agree to use medically approved contraceptive methods during the study and for 90 days post the last dose of study drug:

- Male patients with female partners of child-bearing potential
- Female patients of childbearing potential who have a fertile male sexual partner

Medically approved contraceptives include the following:

- Hormonal contraceptives (oral, transdermal patches, vaginal or injectable),
- Intrauterine device with or without hormones,
- Condom ('barrier' method),
- Diaphragm or cervical cap ('barrier' method),
- Sexual abstinence

6.4. Screen Failures

Individuals who do not meet the criteria for participation in this study (screen failure) may not be rescreened.

7. Treatments

7.1. Treatments Administered

This study involves a comparison of LY3127804 20 mg/kg administered intravenously once every two weeks to placebo. The investigator may withhold the second dose (refer to Section 8.1). Table 7-1 shows the treatment regimens.

Table 7-1. Treatment Regimens

Regimen	Dose Day 1	Dose Day 15
LY3127804	20 mg/kg	20 mg/kg
Placebo	Matching placebo	Matching placebo

Note: Patients weighing 150 kg and above will receive a maximum LY3127804 dose of 3000 mg. Please see the Pharmacy Manual for further instructions.

LY3127804 will be administered as a slow IV infusion over at least 90 (± 15) minutes. Infusion duration may be increased or stopped as deemed necessary based on the institutional standard of care. If an infusion reaction is observed, the patient should be treated according to instructions in Section 9.2.2. Resuscitation equipment and emergency drugs must be available at all times when the patient is being infused. Patients should be observed for at least 60 minutes after completion of the infusion. The actual start and stop time of infusion will be recorded.

The investigator or his/her designee is responsible for the following:

- explaining the correct use of the investigational agent(s) to the site personnel
- verifying that instructions are followed properly
- maintaining accurate records of investigational product infusion and collection
- at the end of the study returning all unused medication to Lilly, or its designee, unless the sponsor and sites have agreed all unused medication is to be destroyed by the site, as allowed by local law.

7.1.1. Packaging and Labelling

The drug product will be manufactured, tested, packaged, and labeled in accordance with all applicable Good Manufacturing Practice (GMP) requirements and country's regulatory requirements. A certificate of analysis confirming the materials are released for human use in clinical trials will be supplied. LY3127804 drug products are for investigational use only and are to be used only within the context of this study.

7.2. Method of Treatment Assignment

Patients who meet all criteria for enrollment will be stratified by age group (<65 years and ≥ 65 years), sex, and site, and then, on Day 1, randomly assigned in a 1:1 ratio within each stratum to receive either LY3127804 or placebo. Treatment assignment will be determined by a computer generated randomization sequence using an interactive web response system (IWRS).

7.2.1. Selection and Timing of Doses

The doses will be administered at approximately the same times on each day. The actual time of all dose administrations will be recorded in the patient's electronic case report form (eCRF).

7.3. Blinding

This is a double-blind study; patients, investigator, and site personnel performing trial related activities or with the ability to influence study outcomes will be blinded with respect to LY3127804 and placebo treatment. To preserve the blinding, all sponsor personnel involved in study conduct will remain blinded to treatment while the study is ongoing, except for individuals (or designee) from Global Patient Safety (GPS) to manage individual serious adverse events and safety reporting. This individual from the GPS team is not involved in day-to-day activities of study conduct. Site staff who are responsible for drug preparation will not be blinded; laboratory personnel will also not be blinded.

After the reporting database is locked for statistical analysis of the double-blind treatment phase, a limited number of sponsor personnel will be unblinded to complete the study report. However, any sponsor personnel continuing with the management and oversight of the study will remain blinded to patients' treatment assignments.

Emergency unblinding may be performed through the IWRS. This option may be used only if the patient's well-being requires knowledge of the patient's treatment assignment. All unblinding events will be recorded and reported by the IWRS.

In case of an emergency, the Investigator has the sole responsibility for determining if unblinding of a patient's treatment assignment is warranted for medical management of the event. The patient's safety must always be the first consideration in making such a determination. If the Investigator decides that unblinding is warranted, it is the responsibility of the Investigator to promptly document the decision and rationale and notify sponsor as soon as possible.

If an investigator, site personnel performing assessments, or patient is unblinded, the patient must be discontinued from the study. In cases where there are ethical reasons to have the patient remain in the study, the investigator must obtain specific approval from a sponsor medical representative for the patient to continue in the study. During the study, emergency unblinding should occur only by accessing the IWRS.

This is a double-blind study.

Upon completion of the study, all codes must be returned to the sponsor or its designee.

7.4. Dosage Modification

Not applicable.

7.5. Preparation/Handling/Storage/Accountability

The investigator or his/her designee is responsible for the following:

- confirming appropriate temperature conditions have been maintained during transit for all study treatment received and any discrepancies are reported and resolved before use of the study treatment.
- ensuring that only patients enrolled in the study may receive study treatment and only authorized site staff may supply or administer study treatment. All study treatments must be stored in a secure, environmentally controlled, and monitored (manual or automated) area in accordance with the labeled storage conditions with access limited to the investigator and authorized site staff.
- the investigator, institution, or the head of the medical institution (where applicable) is responsible for study treatment accountability, reconciliation, and record maintenance (such as receipt, reconciliation and final disposition records).

Detailed instructions for the preparation and handling of LY3127804 and placebo will be provided to the unblinded site pharmacy personnel by the Sponsor.

LY3127804 for Injection vials are to be stored in refrigerated condition (2°C to 8°C).

7.6. Treatment Compliance

All study drug doses will be administered at study site.

7.7. Concomitant Therapy

All concomitant therapies that are part of routine care are allowed and can be used during the study. If indicated, anticoagulation therapies, including full-dose anticoagulation therapies, are allowed.

All concomitant therapies must be recorded in the eCRF.

Concomitant medications captured should include unapproved (“off-label”) medication, such as, for example, convalescent antibodies, remdesivir, chloroquine, hydroxychloroquine, and IL-6 antagonists.

7.8. Treatment after the End of the Study

Study drug will not be made available after conclusion of the study to patients.

8. Discontinuation Criteria

8.1. Discontinuation from Study Treatment

Possible reasons leading to permanent discontinuation of study drug:

- Patient Decision
 - the patient requests to discontinue study drug.
- Investigator Decision
 - The investigator may discontinue treatment after the first dose, if in the judgement of the investigator the benefit/risk assessment for LY3127804 does not support administration of a second dose.
- Grade 3 or higher infusion-related reaction per National Cancer Institute Common Terminology Criteria for Adverse Events (NCI-CTCAE) 5.0 (refer to Section 9.2.2)
- Grade 2 and greater bleeding events associated with study treatment.

Patients discontinuing from the study drug prematurely for any reason should complete adverse event and other follow-up procedures per Section 2 (Schedule of Activities), Section 9.2 (Adverse Events), and Section 9.4 (Safety) of this protocol.

8.2. Discontinuation from the Study

Patients will be discontinued in the following circumstances:

- enrollment in any other clinical study involving an investigational product or enrollment in any other type of medical research judged not to be scientifically or medically compatible with this study
- participation in the study needs to be stopped for medical, safety, regulatory, or other reasons consistent with applicable laws, regulations, and good clinical practice (GCP)
- patient consent withdrawal

Patients discontinuing from the study prematurely for any reason should complete adverse event and other follow-up procedures per Section 2 (Schedule of Activities), Section 9.2 (Adverse Events), and Section 9.4 (Safety) of this protocol.

8.3. Lost to Follow-Up

A patient will be considered lost to follow-up if he or she repeatedly is unable to be contacted by the study site. Site personnel are expected to make diligent attempts to contact patients for the follow-up phone visit.

Site personnel, or an independent third party, will attempt to collect the vital status of the patient within legal and ethical boundaries for all patients randomized, including those who did not get investigational product. Public sources may be searched for vital status information. If vital status is determined, this will be documented and the patient will not be considered lost to follow-up.

Lilly personnel will not be involved in any attempts to collect vital status information.

9. Study Assessments and Procedures

Section 2 lists the Schedule of Activities, with the study procedures and their timing (including tolerance limits for timing).

Appendix 2 lists the laboratory tests that will be performed for this study.

Appendix 4 provides a summary of the maximum number and volume of invasive samples, for all sampling, during the study.

Unless otherwise stated in the subsections below, all samples collected for specified laboratory tests will be destroyed per local site procedures.

9.1. Efficacy Assessments

9.1.1. Primary Efficacy Assessments

Ventilator free days will be defined as the number of days from Day 1 to Day 28 on which a patient does not require a ventilator (IMV), if the period of breathing without a ventilator (IMV) lasted at least 24 consecutive hours and the patient did not die within 28 days from first dose of study drug; if the patient died within 28 days, then this end point will be set equal to -1.

9.1.2. Secondary Efficacy Assessments

9.1.2.1. NIAID Ordinal Assessment

The NIAID will be assessed daily and defined as the lowest score achieved for that day [[NCT04280705](#)].

- 1- Death
- 2- Hospitalized, on invasive mechanical ventilation or extracorporeal membrane oxygenation (ECMO)
- 3- Hospitalized, on non-invasive ventilation or high flow oxygen devices
- 4- Hospitalized, requiring supplemental oxygen
- 5- Hospitalized, not requiring supplemental oxygen - requiring ongoing medical care (COVID-19 related or otherwise)
- 6- Hospitalized, not requiring supplemental oxygen - no longer requires ongoing medical care
- 7- Not hospitalized, limitation on activities and/or requiring home oxygen
- 8- Not hospitalized, no limitations on activities.

9.1.2.2. Survival Without the Need for Mechanical Ventilation

Proportion of patients who are alive and respiratory failure free (i.e., never having required mechanical ventilatory support; i.e. IMV/ECMO) will be calculated at Day 28.

9.1.2.3. 28-day Mortality

Mortality will be defined as 28-day all-cause mortality, defined as 672 hours from the time of randomization. All patients will be classified as either “alive at Study Day 28” or, if dead, “dead at Study Day 28.”

9.1.2.4. Length of hospital stay

Length of hospital stay will be defined as the number of days hospitalized for at least 1 hour duration.

9.1.3. Exploratory Efficacy Analysis**9.1.3.1. Pulmonary Function**

Pulmonary function will be assessed daily as the range of the average lowest value for SpO₂ and the highest value of O₂ flow rate for that day.

9.1.4. Appropriateness of Assessments

All assessments are widely used and generally regarded as reliable, accurate, and relevant.

9.2. Adverse Events

A clinical trial AE is any untoward medical event associated with the use of a drug or drug delivery system in humans, whether or not it is considered related to that drug or drug delivery system.

Investigators are responsible for monitoring the safety of patients who have entered this study and for alerting the sponsor or its designee to any event that seems unusual, even if this event may be considered an unanticipated benefit to the patient.

The investigator is responsible for the appropriate medical care of patients during the study.

Investigators must document their review of each laboratory safety report and electrocardiogram (ECG).

The investigator remains responsible for following, through an appropriate health care option, AEs that are serious or otherwise medically important, considered related to the investigational product or the study, or that caused the patient to discontinue the study drug before completing the study. The patient should be followed until the event resolves, stabilizes with appropriate diagnostic evaluation, or is reasonably explained. The frequency of follow-up evaluations of the AE is left to the discretion of the investigator.

Lack of drug effect is not an AE in clinical studies, because the purpose of the clinical study is to establish treatment effect.

After the informed consent form (ICF) is signed, study site personnel will record via electronic data capture (EDC) the occurrence and nature of each patient’s pre-existing conditions, including clinically significant signs and symptoms of the disease under treatment in the study. In addition, site personnel will record via eCRF any change in the condition(s) and any new conditions as

AEs. Investigators should record their assessment of the potential relatedness of each AE to protocol procedure or investigational product via EDC.

The investigator will interpret and document whether or not an AE has a reasonable possibility of being related to study treatment, study device, or a study procedure, taking into account the disease, concomitant treatment, and pathologies.

A “reasonable possibility” means that there potentially is a cause and effect relationship between the investigational product, study device, and/or study procedure and the AE.

The investigator will use AE follow-up forms to record additional details regarding AEs related to injection sites and hypersensitivity events.

If a patient’s study drug is discontinued as a result of an AE, study site personnel must report this to the sponsor or its designee via EDC, clarifying if possible the circumstances leading to discontinuation of treatment.

9.2.1. Serious Adverse Events

Study-specific clinical outcomes of progressive pulmonary failure in hospitalized patients with presumed or confirmed COVID-19 are exempt from all serious adverse event reporting unless the investigator deems the event to be related to the administration of study drug. Monitoring by the DMC will include continuous assessment of a potential imbalance in aggregate events between the treatment and control groups (please refer to Section 9.4.5).

The following events will be considered clinical outcomes and not reported as SAEs:

- Death related to progressive pulmonary failure and/or ARDS, that is, related to severe ARDS or a sequela of ARDS based on the interpretation of the investigator.
- Cardiovascular events: cardiac failure.
- Respiratory events: pneumonia, hemoptysis, decreased PaO₂/FiO₂, mechanical ventilation/ECMO, hypoxia, hypoxemia, ARDS, acute lung injury, or respiratory failure.
- Systemic inflammatory response syndrome related criteria: tachypnea, hypopnea, leukocytosis, leukopenia, hypothermia, hyperthermia, tachycardia, or bradycardia.
- Secondary infections

An SAE is any AE from this study that results in one of the following outcomes and is not classified as a clinical outcome of COVID-19 using the definitions shown in Section 9.2.:

- death that is not related to COVID-19 or a sequela of COVID-19 or death that is considered by the investigator to be related to study drug
- prolonged inpatient hospitalization or re-hospitalization life-threatening experience (that is, immediate risk of dying)
- persistent or significant disability/incapacity
- congenital anomaly/birth defect

- important medical events that may not be immediately life-threatening or result in death or hospitalization but may jeopardize the patient or may require intervention to prevent one of the other outcomes listed in the definition above.

The study site personnel must alert the sponsor, or its designee, of any SAE as soon as practically possible but no later than 24 hours.

Additionally, study site personnel must alert the sponsor, or its designee, of any SAE within 24 hours of Investigator awareness of the event via a sponsor-approved method. If alerts are issued via telephone, they are to be immediately followed with official notification on study-specific SAE forms. This 24-hour notification requirement refers to the initial SAE information and all follow-up SAE information.

Although all AEs are recorded in the case report form or EDC after signing informed consent, SAE reporting to the Sponsor begins after the patient has signed informed consent and has received the study drug. However, if an SAE occurs after signing informed consent, but prior to receiving the study drug, AND is considered Reasonably Possibly Related to a study procedure then it MUST be reported.

Investigators are not obligated to actively seek AEs or SAEs in patients once they have discontinued from and/or completed the study (the patient disposition EDC has been completed). However, if the Investigator learns of any SAE, including a death, at any time after a patient has been discharged from the study, and he/she considers the event reasonably possibly related to the study treatment or study participation, the Investigator must promptly notify Lilly.

Pregnancy (maternal or paternal exposure to the study drug) does not meet the definition of an adverse event. However, to fulfill regulatory requirements any pregnancy should be reported following the SAE process to collect data on the outcome for both mother and fetus.

The designated medical monitor of the Sponsor will monitor safety data throughout the course of the study. The Sponsor and/or its designee will review SAEs within appropriate timeframes to meet reporting obligations imposed by regulatory authorities. All serious and unexpected AEs for this study will be reported to regulatory authorities in accordance with local laws, directives, and regulations.

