6.2. Exclusion Criteria

Patients will be excluded from study enrollment if they meet any of the following criteria at screening, until specified otherwise:

1. Have ARDS and/or require immediate intermittent mandatory ventilation (IMV).
2. In the opinion of the investigator, is moribund irrespective of the provision of treatments.
3. Any concurrent serious medical condition (e.g. patients with estimated glomerular filtration rate [eGFR] < 15 mL/min/1.73m² or on dialysis, preexisting lung disease requiring O₂ at rest, a body mass index [BMI] that precludes techniques such as proning) or concomitant medication that in the opinion of the investigator that would preclude participation in the study.
4. Have received treatment with a drug predominantly targeting Ang2 activity (e.g., tyrosine kinase inhibitors and/or antibody treatment) within the past month or 5 half-lives, whichever is longer.
5. Have a known sensitivity to mAbs or other therapeutic proteins, to agents of similar biologic composition as LY3127804, or to any products used in the formulation of LY3127804 (refer to the IB for LY3127804 for details) or are incompatible with the treatment of LY3127804.

6. Have a known history or show evidence of human immunodeficiency virus (HIV) and/or hepatitis A, B or C
7. Exclusion Criterion [7] has been deleted.
8. Have a significant bleeding disorder or active vasculitis or had a Grade ≥ 3 bleeding episode within 12 weeks prior to receiving treatment
9. Have experienced any arterial thromboembolic event, including myocardial infarction, unstable angina, cerebrovascular accident, or transient ischemic attack, within 6 months prior to receiving treatment
10. Have experienced any Grade 3 or 4 venous thromboembolic event that is considered by the investigator to be life-threatening or that is symptomatic and not adequately treated by anticoagulation therapy within 6 months prior to receiving treatment. Patients with chronic portal vein thrombosis who are asymptomatic and not considered to need anticoagulation therapy are eligible.
11. Have chronic congestive heart failure (New York Heart Association class ≥ 3) or uncontrolled cardiac dysrhythmia
12. Have a serious nonhealing: (a) wound, (b) peptic ulcer, or (c) bone fracture, within 28 days prior to receiving first dose of study drug

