4.16 Interim Analyses and Data Monitoring

An independent DMC will review unblinded safety data on an ongoing basis (Protocol Section 9.4.5). These will consist of the following:

- Listing of individual SAEs
- Table of SAEs by treatment group
- Table of TEAEs by treatment group
- Table of NIAID ordinal scale assessment – worst value per patient by treatment group
- Table of demographics by treatment group
- Table of Baseline disease characteristics by treatment group

If the DMC requests and the sponsor agrees to conducting a futility analysis, the conditional power for the primary efficacy analysis will be assessed via simulations, using the data collected so far to predict the remaining data to be collected.

Ongoing monitoring of safety data (including AEs, SAEs, and selected laboratory measurements) will continue throughout the study by the sponsor using blinded data.

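### Protocol 9.2.1 draws the SAE boundary for deaths twice and the two lines disagree, so a fatal event off the exemption list but attributed to COVID-19 has no settled SAE status

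*Protocol*

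**What the plan says.** Protocol 9.2.1 first exempts study-specific clinical outcomes from SAE reporting, unless the investigator deems the event related to study drug. The list that follows has one line about death: "Death related to progressive pulmonary failure and/or ARDS, that is, related to severe ARDS or a sequela of ARDS", as interpreted by the investigator. Its other lines are events: "Cardiovascular events: cardiac failure", a group beginning "Respiratory events: pneumonia, hemoptysis", SIRS-type signs, and secondary infections. Stroke, embolism and bleeding other than hemoptysis are not named.

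The section then defines an SAE as an AE that leads to one of several outcomes and "is not classified as a clinical outcome of COVID-19 using the definitions shown in Section 9.2". The first outcome is a "death that is not related to COVID-19 or a sequela of COVID-19". The same line has a second limb, which keeps any death that the investigator attributes to study drug. Other outcomes, including a life-threatening experience and prolonged hospitalization, carry no COVID-19 qualifier.

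SAE status feeds the 24-hour notice to the sponsor (Protocol 9.2.1), the individual SAE listing and the "Table of SAEs by treatment group" that go to the DMC (SAP 4.16), and the final table of serious treatment-emergent events (SAP 5.1, Table 12).

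**The concern.** The list removes deaths from one disease pathway, lung failure. The death criterion removes deaths from the disease as a whole. Deaths that lie between the two are neither exempt nor SAEs under the death line. Every participant has presumed or confirmed COVID-19 (Protocol 6.1), so attribution to the disease is always open to the investigator.

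The deaths in between include types that the plan watches for. Protocol 6.2 excludes patients who "Have experienced any arterial thromboembolic event, including myocardial infarction, unstable angina, cerebrovascular accident, or transient ischemic attack" within the previous 6 months, and also those with certain recent bleeding or venous events. Protocol 8.1 makes treatment-associated bleeding of Grade 2 or more a reason to stop study drug. For such events one investigator cannot reliably separate drug from disease in a single patient, and comparison by arm is the safeguard. If sites classify them differently, the SAE-based outputs compare incomplete counts.

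**Working it through.** The main check is textual. Each kind of death is taken through both lines of Protocol 9.2.1.

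| Fatal event and attribution | On the exemption list? | Meets the death criterion? | SAE status |
|---|---|---|---|
| Lung failure or ARDS, not drug-related | Yes | No | Not an SAE; the lines agree |
| Cardiac failure or secondary infection, attributed to COVID-19, not drug-related | Yes, as an event | No | Not an SAE; the lines agree |
| Stroke, embolism or non-pulmonary bleed, not attributed to COVID-19 | No | Yes | SAE; the lines agree |
| Any death judged drug-related | Exemption lifted | Yes, by its second limb | SAE; the lines agree |
| Stroke, embolism or non-pulmonary bleed, attributed to COVID-19, not drug-related | No | No | Unsettled |

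Only the last row is affected. Such a death could still be reported as life-threatening. But if that criterion took in every fatal event, the COVID-19 qualifier on the death line would have no effect, and the protocol does not say which line governs. Two sites could read it differently in good faith.

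**What the gap touches.** It touches the three uses of SAE status: the 24-hour notice, the DMC's SAE listing and by-arm table, and the final serious-event table. The SAE listing is the only individual-level safety item named in the DMC's regular package (SAP 4.16).

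**What it does not touch.**
- SUSARs need an investigator judgement of relatedness (Protocol 9.2.1.1), and a death so judged is an SAE by the second limb.
- All AEs are recorded (Protocol 9.2.1), and the sponsor reviews all deaths blinded (Protocol 9.4.5).
- The DMC sees TEAEs and worst NIAID score by arm (SAP 4.16). Score 1 is death, so death counts by arm reach it whatever the attribution.
- The final outputs hold 28- and 60-day all-cause mortality, fatal TEAEs by preferred term, and a listing of all deaths (SAP 4.12.3.3; SAP 5.1, Tables 14, 38 and 39; SAP 5.2, Listing 10).

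**Size.** The plan gives no figure to reproduce. Inputs from Protocol 10.1: 105 patients per group, placebo mortality 12.5%, and a 50% improvement on drug, which gives 6.25%.
- Expected placebo deaths: 0.125 × 105 = 13.1. Expected drug deaths: 0.0625 × 105 = 6.6.
- Assumption, not in the documents: 15-40% of deaths are non-pulmonary.
- Placebo: 13.1 × 0.15 = 2.0 to 13.1 × 0.40 = 5.2, about 2 to 5.
- Drug: 6.6 × 0.15 = 1.0 to 6.6 × 0.40 = 2.6, about 1 to 3.

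These are ceilings. They include cardiac-failure and secondary-infection deaths, which the list already exempts. They also suppose that every remaining death is attributed to COVID-19, judged unrelated to drug, and not reported under another criterion. The planning mortality of 12.5% equals the 25% ARDS rate times the 50% fatality quoted in Protocol 3.1 (0.25 × 0.50 = 0.125). On that basis all the expected deaths are in ARDS patients and the true number could be well below the ceiling.

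**The case against.** The strongest reply is that little is lost. The drug-related limb has a low threshold: Protocol 9.2 defines a reasonable possibility as a potential cause-and-effect relationship, and a death in which drug and disease cannot be told apart may well meet it. A stroke, embolism or major bleed will often qualify as life-threatening or as prolonging hospitalization before it is fatal. Deaths are counted by arm elsewhere.

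Much of this stands, and it limits the point. It does not remove it. The drug-related limb depends on the same single-patient judgement that is hard to make. The life-threatening route is open, but the text does not require it. The sponsor's review is blinded and cannot show an arm difference. The worst NIAID score gives deaths without cause, and the DMC's TEAE table is not stated to show fatal outcome.

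A reader might infer three stronger things that the documents do not support. The first is that every COVID-19 death escapes SAE reporting; the second limb of the same criterion keeps those judged drug-related. The second is that an imbalance in deaths would be hidden from the DMC or that SUSARs would be lost; the items listed in the check show otherwise. The third is that the protocol names thromboembolism as a risk of LY3127804. Protocol 6.2 only excludes patients with such a history, and known risks are left to the Investigator's Brochure. Only bleeding has a treatment-linked rule, in Protocol 8.1.

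**Conclusion.** The inconsistency is real and should be corrected. It is confined to one class: deaths from an event off the exemption list, attributed to COVID-19, and not judged drug-related. For that class Protocol 9.2.1 gives no single answer. Under-reporting as SAEs is permitted by the text but not compelled by it. The consequence is possible incompleteness and site-to-site variation in expedited notice and SAE-based tables, not loss of the deaths from the trial's data. The number cannot be derived from the documents. The range of about 2 to 5 placebo and 1 to 3 drug deaths depends wholly on the assumed 15-40% share and should be read as an upper limit.

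**What to change.** Reconcile the two passages by making the SAE death criterion follow the exemption list as a whole, for example: *any death other than one due to an event on the clinical-outcome list above, and any death judged related to study drug*. The reference must be to the whole list. Excepting only lung-failure and ARDS deaths would turn fatal cardiac failure and secondary infection into SAEs although the same list exempts those events, and so create a new conflict.

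In the same edit, correct the cross-reference in the SAE definition: it points to Section 9.2 for the clinical-outcome definitions, which are in 9.2.1. Carry the wording into the eCRF and SAE-form guidance.

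The cost is one protocol sentence, one cross-reference, matching form guidance and a few additional SAE reports. No analysis method changes.
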